4 STUDY DESIGN

4.1 OVERALL DESIGN

This is an assessor-blinded randomized controlled trial in which patients with well-corrected idiopathic clubfoot will be randomized to wear either their original SB (which is standard care for clubfoot treatment) or the new DB for 30 days. After 30 days, all participants will resume use of the SB and be monitored for an additional 60 days.

This study is a "feasibility trial" as it is assessing the feasibility of conducting a large-scale randomized controlled trial to evaluate the effectiveness of the DB. As such, feasibility will be determined by the ability to recruit patients within the goal study period and to retain participants.

On Day 0 of the study period, patients will be randomized and receive baseline clinical and questionnaire evaluations. A temperature sensor will be added in each participant's boots during the 90-day study period to objectively measure time of brace wear.

All patients will be evaluated after 7 days in their assigned bar to check for brace fit, any complications, and to perform required adjustments. This 7-day checkup is standard care for clubfoot treatment when patients receive the SB and FAB for the first time.

After 30 days, the patients wearing the DB will resume use of the SB. All patients will be seen at the end of the first 30 days and after 90 days to monitor for recurrence of the clubfoot deformity, complications of brace wearing, and parent-reported perception of their child's comfort with the FAB. Parents will also be asked to complete a self-reported brace wear log that will be collected on Day 30 and 90.

A minimum of 10 patients per arm will be recruited. Once there are 10 in each arm, recruitment will halt. It is hypothesized that patients using the DB will experience higher brace tolerance as measured by the temperature sensors, and higher comfort levels as reported by parents, without an increase in clubfoot deformity recurrence compared to the SB.

To compare the range of motion provided by the SB to the DB, and to verify that the DB consistently maintains proper foot position and leg alignment during use, parents will be given the option of consenting to video recordings being taken during the hospital visit of the patient's feet and legs while wearing their prescribed bar. This recording will occur on Day 30 of the study period by a member of the study team. These videos will be closely studied to compare the range of motion provided by the SB to the DB, and to verify that the DB consistently maintains proper foot position and leg alignment during use. Note that audio will be removed from the videos.

Patient recruitment will be documented in an electronic enrollment log. To evaluate ease of recruitment, this enrollment log will also include patients who do not wish to participate in the study and their reason(s) for refusal. The enrollment log will also record information on patients that do not adequately fit the available prototype but are otherwise eligible, including patient age and fit issues. This will serve to inform future adaptations of the new DB.

During the intervention period, all patients will be monitored for brace fit by the PI and/or physiotherapist [name]. A blinded outcomes assessor will clinically evaluate all patients to assess foot shape for possible recurrence or complications. The outcomes assessor will be a skilled clubfoot provider and will not be made aware of which bar was provided to the patient and is

independent of the design team. Once the trial is complete, the patient's care will resume with their primary clubfoot provider.

Clubfoot patients are normally reviewed in clinic every 3-6 months. If scheduling permits, Day 0 of the study period will align with patient's already scheduled follow up visit. All patients will therefore require either 3 or 4 extra visits (possibly on Day 0, and surely on Day 7, Day 30, and Day 90). These extra visits will consist of the same evaluations done in the routine clubfoot monitoring protocol, in addition to the study-related questionnaire, brace wear log, video recording (on Day 30 only), and temperature sensor data collection.

Three surveys will be administered to parents on Day 0, Day 30, and Day 90 of the study period. These surveys will be collected and managed using REDCap (Research Electronic Data Capture) hosted at SickKids. Parents will also be asked to complete a brace wear log to be submitted at Day 30 and Day 90 of the study period.

Most patient information that will be reviewed in this study is data being collected and stored per the REB-approved Clubfoot Research Registry protocol (REB #1000053919). All patients enrolled in study this will also be enrolled in Clubfoot Research Registry, if not already enrolled.

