9 STATISTICAL CONSIDERATIONS

9.1 SAMPLE SIZE DETERMINATION

The intent of this study is to obtain preliminary data on the current prototype and evaluate the feasibility of conducting a larger-scale clinical trial. Therefore, only a minimum of 10 patients will be enrolled in each arm.

In a future effectiveness randomized controlled trial, we plan to use a sample size of 124, with 62 patients per arm. This sample size will ensure that the study has sufficient statistical power to detect a minimal clinically detectable difference in recurrence rates of at least 20% between the SB and DB group. Note this is assuming that the recurrence rates in the control arm will be 30%, as reported recurrence rates after correction range from 20-41% (6). This power analysis was conducted based on 80% power and 5% type 1 error.

The Clubfoot Clinic at SickKids sees approximately 35 patients per week. Based on the frequency of clinical visits required for patients at different stages in the Ponseti treatment, it is expected that approximately 15% of these patients will be between the ages of 1 and 3 and in the minimum 12-hour per day bracing stage of the Ponseti treatment. Furthermore, approximately 80% of all clubfoot patients are idiopathic, and it is expected that 75% of eligible patients will be willing to participate in the trial (22). Therefore, it is foreseen that it will take approximately 2 months to register all 20 participants.

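### Recruiting 20 children in about 2 months is a first pass through a standing clinic pool, so by itself it cannot show that 124 can be recruited

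*Combined protocol and SAP*

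**What the plan says.** Section 4.1 states that "feasibility will be determined by the ability to recruit patients within the goal study period and to retain participants". No numeric cut-off is given for either part. The goal period is not defined separately. The only figure available is the forecast in section 9.1 that "it is foreseen that it will take approximately 2 months to register all 20 participants", repeated as an expected recruitment time in section 4.3. Recruitment stops once each arm has 10.

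The forecast in section 9.1 rests on four inputs:
- "The Clubfoot Clinic at SickKids sees approximately 35 patients per week"
- "it is expected that approximately 15% of these patients will be between the ages of 1 and 3" and in the 12-hour bracing stage
- "approximately 80% of all clubfoot patients are idiopathic"
- "it is expected that 75% of eligible patients will be willing to participate in the trial"

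Under section 5.4, families are approached at regularly scheduled clinic visits. Section 4.1 adds that "Clubfoot patients are normally reviewed in clinic every 3-6 months".

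On the later study, section 9.1 says: "In a future effectiveness randomized controlled trial, we plan to use a sample size of 124, with 62 patients per arm". Section 4.2 gives it at least two years of follow-up. Its accrual period, number of sites and age range are not stated.

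Section 9.3.2 analyses recruitment rate, dropout rate and survey answers descriptively. Neither 9.1 nor 9.3.2 counts distinct eligible children or estimates how many become eligible each year.

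**The concern.** The 35 a week is a flow of attendances. A child reviewed every 3-6 months reappears in it two to four times a year but can be enrolled only once. The pilot is expected to finish in about 2 months, which is inside the first review cycle, when almost every eligible attender is being asked for the first time. After one full cycle the standing pool has been asked, and further recruits come only from children newly reaching the age and brace stage. The pilot therefore observes the fastest accrual the clinic will offer.

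The primary objective is whether a large trial can be recruited. If a met goal period is taken as the answer, the later trial could be planned on a weekly rate that ends after one review cycle. The same early inflation would occur at each clinic of a multicentre trial that recruits from its existing patients.

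**Working it through.** **1. Reproduce the plan's figures.** For 30% against 10%, two-sided 5%, 80% power, no continuity correction:

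n = [1.96 × √(2 × 0.20 × 0.80) + 0.8416 × √(0.30 × 0.70 + 0.10 × 0.90)]² / 0.20² = 61.6, so 62 per arm and 124 in total, as stated.

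Weekly recruitment: 35 × 0.15 × 0.80 = 4.2 eligible visits; × 0.75 = 3.15 willing. Then 20 / 3.15 = 6.35 weeks, or about 1.5 months. This is consistent with a rounded-up 2 months.

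**2. From visits to children.** Distinct children = weekly eligible visits × review interval in weeks.

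| Review interval | Distinct eligible | Willing at 75% |
|---|---|---|
| 3 months (13 weeks) | 4.2 × 13 = 54.6 | 41.0 |
| 6 months (26 weeks) | 4.2 × 26 = 109.2 | 81.9 |

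Both pools are below 124 even at full uptake. Of the exclusions, only idiopathic status is taken into account.

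**3. Chance of at least 20 recruits at the planned inputs.** Two months is read as 8 weeks or as 8.7 weeks (two calendar months). The finite-pool rows let each child be drawn at most once.

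| Model | 8 weeks | 8.7 weeks |
|---|---|---|
| Poisson, mean 3.15 × weeks | 87.5% | 94.0% |
| Binomial on visits (35 a week, 9% each) | 88.6% | 94.8% |
| 55 children, 13-week review, random consent | 94.5% | 98.6% |
| 109 children, 26-week review, random consent | 90.3% | 96.2% |
| 41 willing children, 13-week review | 96.6% | 99.5% |
| 82 willing children, 26-week review | 91.7% | 97.1% |

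Within each finite-pool model the smaller pool passes slightly more often than the larger one. The weekly flow is the same in both, and the check sees only the flow.

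**4. Effect of further exclusions (loss assumed), 8.7 weeks.** A 10% loss gives 85% (Poisson) or 88-93% (finite pool, random consent). A 20% loss gives 69% or 71-76%.

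**5. Time to 124.** Carrying the pilot rate forward: 124 / 3.15 = 39 weeks.

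With replenishment, the assumptions are one site, the same criteria, steady state, and eligibility lasting 2 years (or 3 if age 3 is inclusive). Willing inflow per year = willing pool / years of eligibility. Time = review interval in years + (124 − willing pool) / inflow.

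| Review | Eligibility | Inflow a year | Years to 124 |
|---|---|---|---|
| 3 months | 2 years | 20.5 | 0.25 + 83.05 / 20.5 = 4.3 |
| 3 months | 3 years | 13.7 | 0.25 + 83.05 / 13.7 = 6.3 |
| 6 months | 2 years | 41.0 | 0.5 + 42.1 / 41.0 = 1.5 |
| 6 months | 3 years | 27.3 | 0.5 + 42.1 / 27.3 = 2.0 |

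After the first cycle, weekly accrual would be 0.26-0.79, a twelfth to a quarter of 3.15.

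**The case against.** The strongest reply is that the plan never says 20 children in 2 months proves 124 are recruitable, and never carries 3.15 a week forward. The 2 months is a forecast. Retention, survey answers about joining a future study, and refusal reasons also count. This stands: there is no numeric pass mark, and the pass probabilities above concern recruitment alone. But section 4.1 does tie the feasibility of the large trial to recruiting within the goal period, and nothing else in the plan addresses supply.

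A second reply is that the check is informative. This also stands in part. At 8.7 weeks, with other inputs as planned, uptake of 54% cuts the pass chance to about 50% and uptake of 40% to about 10%. It tests willingness and short-term flow, but not how many children exist.

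A third is that visit frequency was considered, since section 9.1 derives the 15% from it. That sets the eligible share of visits. It does not give a count of children.

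A reader might infer two stronger things. One is that the clinic cannot supply 124. The documents do not support this: only the standing pool is below 124, children keep entering the age band, and with 6-month review the two-year yield under the same assumptions is about 123-143 (65-77 with 3-month review). The age limit is tied to the prototype's size, and the log records fit problems so that the bar can be adapted. The other is that the check passes more than 90% of the time. That depends on the model, on reading 2 months as more than 8 weeks, and on ignoring prototype fit, boot model, English ability, Pirani score and brace intolerance.

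**Conclusion.** The concern holds in limited form. Meeting the goal period would confirm consent and early flow. It would say little about whether 124 children can be found, because a clinic with 55 eligible children and one with 109 would both be expected to pass, at about 87-99% on the planned inputs and less with further exclusions. The gap between 39 weeks and about 1.5-6.3 years shows how far an extrapolated pilot rate could mislead. The longer range rests on an assumed 2-3 years of eligibility, one site, unchanged criteria and steady state. Whether supply would actually fall short cannot be determined from these documents. The point matters because it bears on the primary objective, and it goes beyond a missing detail: the stated criterion does not respond to one of the quantities that decides the answer.

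**What to change.** In sections 4.1 and 9.3.2, report the pilot's weekly rate as an initial rate only, and state that meeting the goal period is not sufficient evidence that 124 can be recruited. Then report:

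- (a) distinct eligible children over one full review cycle;
- (b) uptake at first approach;
- (c) children newly entering eligibility per year.

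Base the recruitment part of the feasibility conclusion on (a × b) + (c × b × accrual years) against 124. Count accrual years from the end of the first review cycle, as in the working. Give a range, state the accrual period and number of sites assumed, and set the result alongside retention. If the projection falls short, the conclusion should be that more sites, a wider age band or longer accrual would be needed.

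The sources are the enrollment log, which tracks children by name and record number, and the Clubfoot Research Registry. Neither may be complete: recruitment may stop before a full review cycle has passed, and the registry holds only enrolled children. A chart count should fill the gaps. The cost is that modest count and a possibly less favourable conclusion; no extra participants or visits are needed.

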4.2 SCIENTIFIC RATIONALE FOR STUDY DESIGN

This trial design allows for direct comparison between SBs and the new DB, without affecting the patient's long-term treatment plan or outcomes. The assessments will be between patients (control vs. experimental cohorts) and within the same patient (experimental cohort wearing both bar designs).

Since participants in this feasibility trial will only use the DB for a maximum of 1 month, the likelihood of finding a difference in bar effectiveness is quite low. Therefore, following this feasibility trial, the study team plans to conduct a prospective randomized controlled trial of the novel DB versus standard bars, comparing the DB's effectiveness at maintaining ideal foot position and preventing recurrence over a minimum two-year period. A separate REB application will be filed for this trial.

Bias in brace wear reporting will also be mitigated in this feasibility study by using temperature sensors to objectively measure the time of brace wear, and by using quantitative evaluations done by blinded outcomes assessors to evaluate study endpoints.

To mitigate the risk of bias in the completion of the parent-reported surveys, the surveys were written using neutral language as much as possible. For example, instead of using the terms "standard" and "dynamic," the bar types were described using the terms "current," "original," and "alternative."

4.3 END OF STUDY DEFINITION

A participant is considered to have completed the study if he or she has completed all phases of the study including the last visit or the last scheduled procedure shown in Section 1.3, Schedule of Activities (SoA). The duration of participation for each individual participant who completes all study visits will be 3 months.

The end of the study is defined as completion of the last visit or procedure shown in the SoA in the trial globally. It is estimated that it will take 5 months from when the study opens to enrollment until the end of the study, as patient recruitment is expected to take approximately 2 months.

5 STUDY POPULATION

5.1 INCLUSION CRITERIA

In order to be eligible to participate in this study, an individual must meet all of the following criteria:

- 1. Ability of parent/care giver to complete brace wear log/surveys in English
- 2. Diagnosis of idiopathic clubfoot (unilateral or bilateral).
- 3. Current use of a SB with their Foot Abduction Brace.
- 4. In the minimum 12-hour per day bracing stage of the Ponseti treatment
- 5. Aged 1 to 3 years (as the DB prototype was designed based on the average size and strength of a child within that age group).
- 6. Well-corrected clubfoot/clubfeet (Pirani score ≤ 0.5)
- 7. Enrollment in the SickKids Clubfoot Research Registry.

5.2 EXCLUSION CRITERIA

An individual who meets any of the following criteria will be excluded from participation in this study:

- 1. Recurrent clubfoot deformity at time of recruitment and/or Day 0 in study period:
 - Pirani score above 0.5
 - Presence of cavus, adduction, or hindfoot varus
 - Less than 10 degrees of passive ankle dorsiflexion
- 2. Current complaint of significant brace intolerance.
- 3. Any condition or diagnosis, that could in the opinion of the Principal Investigator or delegate interfere with the participant's ability to comply with study instructions, might confound the interpretation of the study results, or put the participant at risk, i.e., skin conditions such as eczema, neurologic conditions or any non-idiopathic clubfoot, any acute or chronic illness perceived to be causing the child discomfort such as a cold or flu or other concurrent painful procedure.
- 4. The patient does not adequately fit the available prototype, e.g., shoulder width distance is too narrow or wide for prototype bar width. However, these patients will be recorded in the study enrollment log to identify the size of this subset. The age and fit issues of these patients will also be recorded to allow future adaptations of the new DB to accommodate this subset.
- 5. The patient is using an older boot model, in which a temperature sensor cannot be inserted, and the patient does not adequately fit the available boots, in which the temperature sensors have already been installed.

5.3 SCREEN FAILURES

Individuals who consent to participate in the clinical trial, but do not meet the criteria for participation in this trial, may be rescreened after 1 week to a maximum of 3 times. Rescreened participants should be assigned the same participant number as for the initial screening.

5.4 STRATEGIES FOR RECRUITMENT AND RETENTION

During the patient's regularly scheduled visit to the Hospital for Sick Children, parents will be asked by their clubfoot provider if they are interested in potentially participating in the trial. Should they be interested, further explanation will be provided by a member of the research team.

Since all participants will be 3 years or younger, patients will not have capacity to consent or assent for themselves. Therefore, parent consent will be sufficient for this study. Consent will be obtained by the research assistant and/or research coordinator and captured via an online REDCap form. For each new consent, a paper 'Consent Discussion Form' will be completed.

Patient recruitment will also be documented in an electronic enrollment log. This enrollment log will also include patients who do not wish to participate in the study and their reason(s) for refusal. The enrollment log will also record the age and fit issues of patients that do not adequately fit the available prototype but are otherwise eligible. This will serve to inform future adaptations of the new DB.

Participation in this trial is completely voluntary and parents may choose not to participate and may withdraw at any time. If parents choose to withdraw, this will be noted in the study enrollment log. Their collected data will continue to be used in the analysis unless the parent requests otherwise.

As an incentive for visit attendance, all participants will receive \$20 CAD for each extra clinical visit (possibly on Day 0, and surely on Day 7, Day 30, and Day 90 of the study period) as compensation for travel expenses, given on the day of the final study visit.

6 STUDY INTERVENTIONS

6.1 STUDY INTERVENTION DESCRIPTION

An example of a straight SB is the Ponseti bar, which is a rigid, metal bar that clips on and off of the patient's boots by means of a patented "Quick Clip" mechanism (15). This bar is available in 3 sizes, depending on the patient's shoulder width. Designated as a class 1 medical device, this bar is used as standard care for clubfoot treatment (16).

The DB prototype is a 3-part bar, consisting of a crossbar with two L-shaped components on each end, which connect to the boots by the same "Quick Clip" mechanism. Each L-component is connected to the crossbar via a low friction slider, which allows for independent axial translation perpendicular to the crossbar, and a modified ball joint linkage, which allows for independent sagittal rotation.

The ball joint linkages also provide a small amount of independent axial and coronal rotation. This provides the patient with extra ankle dorsiflexion and abduction up to a maximum of 30 degrees in each direction. This allows for added movement through the knee and hips, reduces strain at the patient's joints, and reduces stress concentration at the hinges of the bar.

The L-components are machined using 5052-H32 aluminum and have a soft protective end cap to reduce the risk of any unintentional self-injuries. The crossbar and sliders are 3D printed using medical grade ABS plastic. They are attached using adhesive, two steel ball joint linkages, and various fasteners made out of steel and brass.

Ideal foot position for clubfoot is approximately 10 degrees of ankle dorsiflexion, and 60 degrees of external rotation with the feet held shoulder-width apart. This position is maintained as the DB is prebent to provide 10 degrees of ankle dorsiflexion, the external rotation can be adjusted with bolts, and the length of the bar can be adjusted with set screws. While the DB provides extra mobility, the ball joint linkages prevent patients' ankle dorsiflexion of less than 10 degrees and abduction of less than 60 degrees at all times during use. We anticipate that providing patients with more ankle dorsiflexion and external rotation than required will have no negative effects on patient outcomes.

The DB is compatible with the same boots as other SBs. Images of the Ponseti SB and the new DB can be found in Appendix A.

Since each DB prototype will be used on 2 patients during the trial, it will undergo cleaning and disinfection between patients. The Infection Prevention and Control department at SickKids confirmed that the use of CaviWipes, which is a hospital approved low level cleaner/disinfectant, will suffice for this device.

